### Outcomes:

- Anxiety: *State-Trait Anxiety Inventory (STAI-YI)* This 20 item self-report measure indicates the intensity of feelings of anxiety; it distinguishes between state anxiety (a temporary condition experienced in specific situations) and trait anxiety (a general tendency to perceive situations as threatening). This uses a 4 point visual analog scale and the participant indicates how they feel in the moment (1=not at all to 4=very much so).
- Brief Resilience Scale (6 item): This brief 6 item survey is a validated way to assess resilience (ability to bounce back or recover from stress). It uses a 5 point visual analog scale to measure ability to bounce back where 1 is 'strongly disagree' and 5 is 'strongly agree' with a resilience focused statement.

- Human (7 items): This form has been developed by the Reulay sponsor and is used by the sponsor to individualize the Virtual Reality Experience to each person depending on the issues the person needs addressed. It provides 7 options and the participant will indicate the level of which each item is a current issue from 1= not at all to 5=a great deal. For this study, we will administer this questionnaire and evaluate the participant response to the two VR experiences based on how they responded to this survey.
- Emotional Distress: Adapted from the Emotional Distress-short form 7a (7 items). The *PROMIS Anxiety* item banks assess self-reported fear (fearfulness, panic), anxious misery (worry, dread), hyperarousal (tension, nervousness, restlessness), and somatic symptoms related to arousal (racing heart, dizziness). Anxiety is best differentiated by symptoms that reflect autonomic arousal and experience of threat. Only one behavioral avoidance item is included in the adult item bank; therefore, behavioral fear avoidance is not fully evaluated. The anxiety measures are universal rather than disease-specific. The original adult short form (7a), which is being used in this study was constructed by the domain team with a focus on representing the range of the trait and also representing the content of the item bank. Domain experts reviewed short forms to give input on the relevance of each item. Psychometric properties and clinical input were both used and likely varied in importance across domains. Each item on the measure is rated on a 5-point scale (1=never; 2=rarely; 3=sometimes; 4=often; and 5=always) with a range in score from 7 to 35 with higher scores indicating greater severity of anxiety. The original form instructed participants to think about the past seven days, but for purposes of this study, we will reword the question to focus on the current time ('now'). Therefore due to the change in directions of the reference point, our version of this measure is unvalidated and cannot be compared to the general population.
- Cognitive Function short form 6a (6 items) : The *PROMIS Cognitive Function and Cognitive Function Abilities Subset* item banks assess patient-perceived cognitive deficits. Facets include mental acuity, concentration, verbal and nonverbal memory, verbal fluency, and perceived changes in these cognitive functions. The extent to which cognitive impairments interfere with daily functioning, whether other people observe cognitive impairments, and the impact of cognitive dysfunction on quality of life are also assessed.
- Self-efficacy (Short Form 4a – 4 items): This *PROMIS Self-efficacy Scale* defines self-efficacy as confidence in one's ability to successfully perform specific tasks or behaviors. It assesses confidence in one's ability to successfully perform specific tasks or behaviors related to one's health in a variety of situations. Each item on the measure is rated on a 5-point scale (1=I am not at all confident; 2=I am a little confident; 3=I am somewhat confident; 4=I am quite confident; 5=I am very confident)
- Satisfaction with the program: This questionnaire is adapted from *Was it Worth it Questionnaire (WIWI)* and the *Reulay Qualitative Survey (RQS)* to measure study and RV satisfaction. It will be administered to the participants prior to discharge after completing the intervention at the end of the study, probing their satisfaction with the research study. These data could be used to assess the feasibility of the intervention by asking the patient if the entire research experience was worth it for them.

#### Acceptability and Adherence to Intervention:

- Acceptability will be measured through the patient satisfaction survey at the end of the study.
- Adherence to the R-VR will be assessed by collecting attendance for study visits 1-4.

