### Study Design and Methods

**Design:** This is a single blinded randomized cross-over study. The participants will be randomly assigned the order of the paradigms viewed in the R-VR or as videos on the computer. The randomization will be through REDCap, as programmed by the study statisticians. The R-VR with the pre-programmed paradigms and corresponding non-VR videos will be labelled A through D. The coordinators will be informed via REDCap about which the experience to provide the participants for each of the study visits: A-D for Visits 1-4.

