## Visit Flow and Timeline

Visit Number	Day 0	Day 1		Day 4		Day 7		Day 10	
	V0 	V1a 	V1b	V2a	V2b	V3a	V3b	V4a	V4b
		Consent + 0 day to +7 days from	Immediately following VR/Video	Prior to VR/Video	Immediately following VR/Video	Prior to VR/Video	Immediately following VR/Video	Prior to VR/Video	Immediately following VR/Video
Informed Consent	X 								
Inclusion/Exclusion	X								
Demographics Form	X								
Medical History	X								
Adverse Events	X	X		X		X		X	
Concomitant Medications	X	X		X		X		X	
R-VR Intervention			X		X		X		X
Brief Resilience		X		X		X		X	
Evaluate Response to the VR experience (HUMAN)		X	X	X	X	X	X	X	X
Emotional distress		X	X	X	X	X	X	X	X
Cognitive Function		X	X	X	X	X	X	X	X
Self-efficacy		X		X		X		X	
Anxiety		X	X	X	X	X	X	X	X
Satisfaction Survey									X

Consent can be completed digitally in person or through remote consenting

Visit 0 and Visit 1 can occur on same day or on separate occasions at the participant's convenience.

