### Data Analysis

**Power Statement:** The sample size for this pilot investigation (N=24) was established after considering both the statistical implications and the amount of project effort and resources required to recruit and study this unique participant population.

**Data Analysis Plan:** Data related to participant recruitment will be summarized, including the frequency of calls and the reasons for failing screening criteria. In all cases, data will be summarized using mean  $\pm$  SD for continuous variables and frequency percentages for nominal variables. Details will be documented and summarized for any participants who experience adverse events or are unable to complete the 10-minute VR experience for any reason. The percentage of participants who undergo the initial VR experience (V2) but discontinue study participation without returning for the 2nd VR experience (V3) will be summarized and compared between scenes using Fisher's exact test. Anxiety, stress, cognition will be assessed immediately before/after and 24 hours following each VR experience. Within and between group comparisons will be performed using appropriate repeated measures analyses (e.g. paired t-test, repeated measures ANOVA) taking into account the two group repeated measures cross-over study design. In all cases, findings will be summarized using point estimates and corresponding 95% confidence intervals.

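### VR drop-out is tied to V2 and V3 although order is randomised, VR adherence counts video visits, and acceptability is asked only of those who reach the last visit

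*Combined protocol and SAP*

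**What the plan says.** All references are to the combined protocol and SAP.

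- **Order of experiences (Study Design and Methods).** "The participants will be randomly assigned the order of the paradigms viewed in the R-VR or as videos on the computer". The "pre-programmed paradigms and corresponding non-VR videos will be labelled A through D", and coordinators learn through REDCap "about which the experience to provide the participants for each of the study visits: A-D for Visits 1-4". The Resources section lists two VR devices, one per paradigm, and a computer for the rest. The Video Experience Procedure section describes two scenes in each modality. Each participant therefore has two VR and two video sessions.
- **Drop-out (Data Analysis).** The measure is the percentage of participants who "undergo the initial VR experience (V2) but discontinue study participation without returning" for the second VR experience, which is labelled V3. It is compared between scenes with Fisher's exact test. The same section also documents those who "are unable to complete the 10-minute VR experience for any reason".
- **Adherence (Acceptability and Adherence to Intervention).** "Adherence to the R-VR will be assessed by collecting attendance for study visits 1-4".
- **Acceptability (same section).** "Acceptability will be measured through the patient satisfaction survey at the end of the study". In the Visit Flow and Timeline table, the "Satisfaction Survey" row has a single mark, at V4b. The Outcomes section places the survey once the intervention is finished.

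Adherence is primary aim 2, and acceptability is part of primary aim 1.

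**The concern.** The visit numbers in the drop-out measure conflict with the randomised order. The words for the first and second VR experience are right, but an analyst who follows the visit numbers would obtain a different count from one who follows the words.

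The adherence measure mixes VR and video visits. Someone who attends all the videos and misses a VR session counts as three-quarters adherent, and someone who attends but cannot finish a VR session counts in full.

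The acceptability survey does not reach anyone who leaves before V4b. Partial completion is foreseen, because payment is prorated by visits completed. If people leave because they dislike or cannot tolerate VR, the result is too favourable. If leaving is unrelated to acceptance, it is not biased.

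The aims section says the pilot will inform whether to go on to a larger study with more VR per day. That decision needs VR-specific exposure, drop-out counted from the right sessions, and the number of VR-exposed people whose view is unknown.

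**Working it through.** The documents give no drop-out rate, sequence list or planned adherence figure, so there is no stated number to reproduce. N = 24 randomised, four visits, and two VR plus two video sessions come from the documents. Every rate below is an assumption.

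**1. Visit labels.** Four experiences can be ordered in 4! = 24 ways. The two VR sessions can occupy visits (1,2), (1,3), (1,4), (2,3), (2,4) or (3,4), each in 4 of the 24 orders. With all orders equally likely:

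- VR at exactly V2 and V3: 4/24 = 16.7%.
- First VR session at V1 in 12, at V2 in 8 and at V3 in 4.
- At least one video visit between the two VR sessions: 12/24.

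The literal V2-to-V3 rule can be compared with the true state (one VR session had, second missed):

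| Leaves after | Flagged by literal rule | Had exactly one VR session |
|---|---|---|
| V1 | no | 12/24 |
| V2 | yes | 16/24 (4/24 had none, 4/24 had both) |
| V3 | no | 12/24 |

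Under restricted schemes (also assumed), the labels fit:

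- 0% if modality is blocked or strictly alternated;
- 0% or 50% in a four-sequence Williams square (ABDC, BCAD, CDBA, DACB), depending on which letters are VR;
- 100% only if everyone has video-VR-VR-video, in which case the order of modality is not random.

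**2. Adherence.** Let the VR sessions be at visits i < j, with the six patterns equally likely.

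*Leaving after VR.* With probability p of staying after each VR session, expected four-visit attendance is the mean of [i + p(j − i) + p²(4 − j)]/4. Over the six patterns, i sums to 10, j − i to 10 and 4 − j to 4, so the mean is (10 + 10p + 4p²)/24. VR sessions started are (1 + p)/2.

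*Skipping VR visits.* With probability s of skipping a VR visit and all video visits kept, attendance is [2 + 2(1 − s)]/4 and VR attendance is 1 − s.

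| Assumed loss | Leaving: four-visit attendance | Leaving: VR started | Skipping: four-visit attendance | Skipping: VR attended |
|---|---|---|---|---|
| 10% | 92.7% | 95% | 95% | 90% |
| 20% | 85.7% | 90% | 90% | 80% |
| 30% | 79.0% | 85% | 85% | 70% |

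*Loss unrelated to modality.* With 10% lost between successive visits, attendance is (1 + 0.9 + 0.81 + 0.729)/4 = 86.0%. The VR figure averaged over the six patterns is the same.

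**3. Acceptability.** If 2, 4 or 6 of 24 leave before V4b, the survey can cover at most 22/24 = 91.7%, 20/24 = 83.3% or 18/24 = 75.0%. No scoring of the survey is given, so the size of any bias in the result cannot be calculated.

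**The case against.** The label conflict is narrow. The sentence names the first and second VR experience in words, and an analyst holding the REDCap sequence could count correctly. That is true, but the visit numbers are still in the text and lead to a different count.

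On adherence, the visit table marks the R-VR row at all four visits under VR/Video column headings, so the term might be read as the whole four-session programme. Elsewhere the document separates R-VR from video, so the term is at best ambiguous. The split by modality can be recovered afterwards from attendance and the assigned sequence, so no data are lost. In the leaving scenarios the gap is only 2.3 to 6.0 percentage points, about 1 to 3 of the 48 VR sessions (24 × 2). The larger gaps require participants to skip VR visits selectively, which presumes they know the modality beforehand, and nothing says they are told. All of this limits the weight of the point. It remains that the planned figure for a primary aim is not specific to VR.

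On acceptability, an end-of-study survey is a common choice in a short pilot, the bias is conditional on why people leave, and those who withdraw may not answer. The planned summaries of incomplete sessions and drop-out would show part of the loss. They would not supply those participants' ratings, which cannot be recovered later.

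It can also be said that no form records the start of a session. This is largely met, because details are to be documented for anyone who does not complete VR, whatever the reason.

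**Conclusion.** The concern holds on all three parts, with unequal weight.

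- **Drop-out labels:** wrong as written. Both are correct in 17% of orders if all 24 are equally used, and for everyone only under one modality pattern that the design section does not state.
- **Adherence:** the stated measure does not isolate VR. The error can go in either direction and is zero if loss is unrelated to modality. It is a reporting gap that can be repaired from data already planned.
- **Acceptability:** the result describes completers only, and this is the one part that cannot be repaired afterwards. The size and direction of any bias are unknown.

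The percentages rest on assumed sequences and loss rates. Because the documents set no threshold for going on to a larger study, no change in that decision can be shown. The sample size is not affected.

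**What to change.** 1. **Data Analysis.** Replace V2 and V3 with each participant's first and second VR session according to the assigned sequence. List the last experience attended before leaving, because a video visit can lie between the two VR sessions.
2. **Acceptability and Adherence to Intervention.** Report adherence to the R-VR as VR sessions started and VR sessions completed, each out of two. Report four-visit attendance separately. The record of an incomplete session should separate a session never begun from one stopped early.
3. **Visit Flow and Timeline, Outcomes, and Acceptability and Adherence to Intervention.** Give the satisfaction survey also at early withdrawal, using the email or telephone route already described under Data Collection. Report acceptability with the number of non-responders among those who started at least one VR session. Add best- and worst-case bounds only if a yes/no acceptability item is defined in advance.

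The cost is wording changes in four sections and one extra REDCap survey trigger. Attendance by visit, assigned experience and incomplete VR sessions are already to be recorded, so the first two changes need essentially no new data. The downsides are one more contact at withdrawal and a possibly less favourable acceptability figure. The definitions should be fixed before the data are seen.

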#### Resources

REDCap will be utilized for data collection using created online forms. Clinician investigators will provide medical oversight. Tools needed for this intervention include one R-VR for each paradigm for a total of 2 R-VRs and a computer for the non VR experiences.

## **Study Design**

We will use standardized procedures to ensure uniform instructions and support for all participants for the recruitment, screening, and study entry.

## **Recruitment**

Participants will be recruited from Mayo Clinic healthcare professionals. We propose to recruit, consent and screen a convenient sample of 36 participants through IRB approved contact materials in order to enroll 24 to study. All participants who respond to the recruitment message will be pre-screened for inclusion and exclusion criteria via a telephone pre-screen. Those who meet criteria will be invited to a consent visit followed by a study screening visit. After consent and screening has taken place, participants who meet all study entry criteria will be invited to participate in the study.

## **Consent and Screen**

Study coordinator will discuss possible participation with the potential participant who has expressed an interest in the study. The study coordinator will begin by introducing the study details, and after determining that the participant has continued interest in study participation, will move on to the study consent. If the participant chooses to consent, the study coordinator will screen the participant for study entry inclusion/exclusion criteria. If study entry criteria are met, the participant will begin their study participation. They will be asked to complete the study surveys/questionnaires, and after this is completed the participant will be instructed on the R-VR device and the video viewing experiences.

## **Video Experience Procedure**

Participants will be scheduled for a 30-min office visit. After a verbal description of the study process and completion of IRB consent form, participants will complete the demographic and other baseline questionnaires.

The coordinator will instruct the participant on certain procedures dependent on the study participant's randomization and visit:

**R-VR Experience:** Study participant will be asked to complete a set of questionnaires, following completion they will be seated in a swivel chair in the center of the research room, given basic instruction on the VR headgear [*Oculus Quest*], and then offered the opportunity to experience the intervention event. The approximately 10 minute VR event involves one of two scenes (randomly selected by REDCap): Scene 1 is designed for relaxation in nature with natural scenery such as trees, streams and deer, or Scene 2 designed to help the participant focus with natural scenery such as glowing embers and fireflies. After a VR experience, the headgear will be removed and the participants will be asked to complete a second round of questionnaires.

**Computer Video Experience:** Study participant will be asked to complete a set of questionnaires, following by being seated at a computer and asked to watch a video with one of two scenes: (Scene 1) natural scenery such as trees, streams and deer; (Scene 2) natural scenery such as glowing embers and fireflies. After this viewing they will be asked to complete a set of surveys.

All will be remunerated up to \$40 at the end of their study participation. This amount will be prorated based on the number of visits completed

This process will provide a within-participant control, allowing us to investigate whether the VR experience is safe and results in significantly more change than the Video experience.

## **Participant Information**

**Target accrual:** 24 to be randomized (36 to be consented and screened).

**Participant population:** 24 adults

**Inclusion Criteria:**

1. 18 years of age or older at the time of consent
2. Healthcare Professional at Mayo Clinic
3. Not pregnant by participant self-report at time of consent
4. Have the ability to provide informed consent
5. Have no contraindicated comorbid health conditions as determined by the clinical investigators

**Exclusion Criteria:**

1. Currently (within the past 3 weeks) been practicing mindfulness training on a weekly/regular basis
2. Currently (within the past 3 weeks) been undergoing an additional program (e.g. CAM) to improve quality of life
3. Currently (within 3 weeks) been enrolled in another clinical or research program (e.g. CAM) which impacts the patients' QOL, stress or anxiety
4. Currently has photosensitivity
5. Cannot tolerate virtual reality experiences
6. An unstable medical or mental health condition as determined by the physician investigator (e.g. pre-existing eye strain, seizures, dizziness, nausea)

### Data Analysis

**Power Statement:** The sample size for this pilot investigation (N=24) was established after considering both the statistical implications and the amount of project effort and resources required to recruit and study this unique participant population.

**Data Analysis Plan:** Data related to participant recruitment will be summarized, including the frequency of calls and the reasons for failing screening criteria. In all cases, data will be summarized using mean  $\pm$  SD for continuous variables and frequency percentages for nominal variables. Details will be documented and summarized for any participants who experience adverse events or are unable to complete the 10-minute VR experience for any reason. The percentage of participants who undergo the initial VR experience (V2) but discontinue study participation without returning for the 2nd VR experience (V3) will be summarized and compared between scenes using Fisher's exact test. Anxiety, stress, cognition will be assessed immediately before/after and 24 hours following each VR experience. Within and between group comparisons will be performed using appropriate repeated measures analyses (e.g. paired t-test, repeated measures ANOVA) taking into account the two group repeated measures cross-over study design. In all cases, findings will be summarized using point estimates and corresponding 95% confidence intervals.

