### Data Collection

- Participants will complete study surveys/questionnaires through REDCap. The coordinator will provide the iPad digital or paper copy version of the survey/questionnaire to the participant for the in-person visits and by email link or phone interview for the remote visits.
- Survey data collection in this study will utilize REDCap. The only anticipated paper source documents will be if participant chooses to complete surveys via paper copy or phone collection, which will then have select variables entered directly into the REDCap data entry system. All other data collection will be entered directly into this password protected system.

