## Assessments

### Study Entry Screen/Safety:

- Demographics Form: This form will collect demographics (age, sex, education, marital status, job title), and other lifestyle history of the research participant.
- Medical History Form: This form will collect history of comorbid conditions such as head injury, seizures, major mental illness or anything that could interfere with the VR experience (e.g. eye sight). This information will be collected via self-report and health record abstraction.
- Adverse Events: Pre-post measures will be obtained for dizziness; stomach awareness; headaches; eyestrain and lightheadedness; nausea; seizures in individuals with photosensitivity; disorientation; temporary (short term) loss of spatial awareness.
- Concomitant Medications: Current medications (name, dosing, and indications) will be collected at every patient encounter.

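### No symptom check is scheduled after a participant's last attended session, so delayed or persisting VR symptoms can go unrecorded although safety is a primary aim

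*Combined protocol and SAP*

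**What the plan says.** Four parts of the combined protocol and SAP bear on this.

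- **Visit Flow and Timeline.** The Adverse Events row is marked at V0, V1a, V2a, V3a and V4a. None of the post-session columns (V1b to V4b) is marked, and no column follows V4b.
- **Study Entry Screen/Safety.** The adverse-event entry promises a before-and-after comparison: "Pre-post measures will be obtained for dizziness; stomach awareness; headaches; eyestrain and lightheadedness; nausea", followed by further symptoms.
- **Data Analysis Plan.** It states "Details will be documented and summarized for any participants who experience adverse events or are unable to complete the 10-minute VR experience for any reason". Participants who have the V2 experience and do not come back for V3 are reported as a percentage, which "will be summarized and compared between scenes using Fisher's exact test". Reasons are named only at the recruitment stage: "Data related to participant recruitment will be summarized, including the frequency of calls and the reasons for failing screening criteria". The same paragraph plans an assessment of anxiety, stress and cognition 24 hours after each VR experience.
- **Data Collection.** Questionnaires may be completed "by email link or phone interview for the remote visits". The schedule shows no remote assessment visit; its only remote element is the option to consent remotely.

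Under Acceptability and Adherence to Intervention, adherence is attendance over the four visits, and acceptability is the end-of-study satisfaction survey. The schedule places that survey at V4b only.

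**The concern.** Safety and acceptability come first among the primary aims, and the pilot is meant to inform a decision on a larger study with longer daily VR exposure. Tolerability is therefore one of its main products.

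Under the schedule, the question about symptoms after one session is put at the start of the next visit. That works for sessions one to three in people who return. It does not work for the fourth session in anyone, or for the last session of anyone who leaves early. A headache or disorientation that begins or persists after the participant has left the room then has no planned route into the data. The reported rate of delayed symptoms would be too low by an unknown amount, and a zero count could not be read as absence. Early leavers also miss the satisfaction survey, so the plan provides neither a late symptom report nor an acceptability rating from them.

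**Working it through.** The plan states no figure for this point. N = 24 is given without a dropout rate, so the sizes below are illustrative.

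**Step 1. When symptoms are asked about.** Visits are at days 1, 4, 7 and 10.

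| Situation | Immediate symptoms | Delayed or persisting symptoms |
|---|---|---|
| Sessions 1 to 3, participant returns | Pre-post measures, if the safety section is followed | Asked before the next session, about 3 days later |
| Session 4, any participant | Same | No scheduled question |
| Any session followed by non-return | Same | No scheduled question |

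The immediate column depends on which section staff follow. The safety section promises post-session measures, and the schedule has no post-session mark for adverse events. The 24-hour assessment does not fill the last column, because symptoms are not among its listed contents and the schedule does not carry it.

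**Step 2. How many VR sessions lack a later question.**

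- Inputs: "24 to be randomized (36 to be consented and screened" (Participant Information), so 24 participants; four experiences each, two of them VR (Design).
- VR sessions: 24 × 2 = 48.
- Assumption: order is balanced, so half of participants have a VR experience at V4. VR sessions at V4: 24 × 2/4 = 12.
- Share: 12/48 = 25%.
- Range without that assumption: each participant has one V4 session, so the count lies between 0 and 24 of 48, or 0% to 50%. The Design section says the order is random but does not say it is balanced.
- Each participant who leaves directly after a VR session before V4 adds one more such session.

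**Step 3. What the gap could hide.**

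- With no withdrawals, balanced order and no delayed symptom reported after the other 48 − 12 = 36 VR sessions, the per-session proportion with a delayed symptom lies between 0 and 12/48 = 25%.
- For withdrawals, let d of 24 leave with unknown later symptoms. Take the others as fully ascertained and event-free. The participant-level proportion lies between 0 and d/24: 1/24 = 4.2%, 3/24 = 12.5%, 6/24 = 25%. The values of d are assumed.
- For d = 3, the exact 95% upper limit from the 21 observed is 1 − 0.025^(1/21) = 16.1%, giving 0 to 16.1%. If all three had a symptom, 3/24 gives 2.7% to 32.4%. With everyone followed and no event, 1 − 0.025^(1/24) = 14.2%, giving 0 to 14.2%.

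These are bounds, not expected values.

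**The case against.** The case against is substantial, and much of it stands.

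1. **There may be contact after V4.** The 24-hour assessment and the remote collection route, read together, plausibly describe a remote contact the day after every VR session, including one at V4. A reader of the schedule alone might infer that nothing happens after V4b, or that a quarter of VR sessions have no later contact. The Data Analysis Plan does not support that. What is missing is a scheduled symptom question, because symptoms are not listed at 24 hours.

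2. **Immediate sickness is covered.** The pre-post measures and the documentation of adverse events and unfinished VR sessions would record sickness during or just after the last attended session, and that record can be linked to non-return. A reader might infer that the plan cannot tell VR sickness from an unrelated reason for leaving. That is too strong. What stays unresolved is a completed session with nothing recorded, followed by non-return.

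3. **Silence is not prohibition.** Nothing stops staff from asking a leaver why, and some pages, including consent pages, are not in the reviewed text. It would be wrong to say that leavers are never asked; the available text simply makes no provision for asking.

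4. **Leavers may not be the symptomatic ones.** It is plausible that they are, but the documents give no evidence, and this point does not rely on it.

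5. **The weak between-scene test is a separate matter.** With an assumed 12 per scene, 3 withdrawals against 0 gives two-sided Fisher p = 2 × 220/2024 = 0.217. That says nothing about whether symptoms are sought. The split is also uncertain: with four experiences in random order, V2 need not be a participant's first VR session. The plan further promises estimates with 95% intervals, so the result does not rest on a p-value.

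**Conclusion.** The concern holds in a limited form. Delayed or persisting symptoms after a participant's last attended session (V4 for completers, earlier for those who withdraw) have no scheduled ascertainment, although safety is part of the first primary aim. The safety section, the schedule and the Data Analysis Plan also disagree on what is collected after a session and must be reconciled.

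Under balanced order, about 12 of 48 VR sessions (25%) lack a later scheduled symptom question; without that assumption the range is 0% to 50%. VR sessions followed directly by withdrawal come on top, in a number the documents do not allow one to predict. The reading of the schedule rests on the table as extracted from the PDF.

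The missing reason for leaving would, taken alone, be only a missing detail. It is worth adding because the same contact can collect it. No planned estimate is shown to be wrong. This is a cheap improvement in safety ascertainment.

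**What to change.** 1. Reconcile Visit Flow and Timeline, the safety assessments and the Data Analysis Plan so that all three state the same post-session adverse-event collection, and give the 24-hour assessment a column in the schedule if it is to be done.
2. Add one short REDCap form, by the existing email-link or phone route, after the last attended session. Send it to all participants after V4 and to anyone who does not return. The 24-hour contact could carry it for completers. Include the symptom list from the safety section, covering the time since that session.
3. On the same form record the reason for leaving, where it applies, and the last experience received.
4. In the Data Analysis Plan, list withdrawals by reason and by last experience (VR or video, and scene). Report how many participants and VR sessions have a symptom report after the last session, so that non-response is visible.

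The cost is a few minutes per participant for 24 people, one form and one schedule line. Sample size and design are unchanged. Some leavers will not answer, so the gap will shrink rather than close.
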